## 1. Study documents, design, objective, and database coding

### 1.1. Introduction

This Statistical Analysis Plan (SAP) is based on the relevant sections of the study protocols CS-BCL-EU2021\_CIP\_V2.0\_21.11.2023\_ITA CH and CS-BCL-EU2021\_CIP\_V2.0\_SubAmend 2\_GERMANY, Version 2.0, released on 21 November 2023.

The current Statistical Analysis Plan (SAP) includes detailed procedures for executing the statistical analysis of the primary and secondary variables and other data.

All analysis data sets, and statistical output will be produced by the statistics department at [name] of 1MED SA using SAS software [1] current version .

### 1.2. Overall Study Design

This is an interventional, post-market, multicentre clinical investigation aimed to enrol patients who require the tumor to be localized in order for the surgeon to perform BCS. The study will include enrollment at 6 centers in Europe. The countries involved are Germany, Italy, Switzerland. The investigation will be useful to collect Investigational Product (IP) performance/safety evidence in Europe.

Each Subject, after signing the Informed Consent Form (ICF), will enter into a screening phase (V0) during which several assessments (e.g., demographics, medical history, blood sample collection, evaluation of available prone MRI and core biopsy pathological results) will be conducted. At visit 1 (V1), the Subject will undergo supine MRI (10-40 days before surgery), from which the 3D breast image and BCL will be made. At visit 2 (V2) the patient will undergo BCS using the BCL System. Soon after surgery and prior discharge, potential AEs will be assessed. On the same day, the

specimen volume will be determined, and the specimen mammogram will be performed. The excised specimen will be sent to the Pathology lab for analysis. The results of the positive margin rate (PMR) will be obtained within 14 days.

At visit 3 (V3), follow-up assessments (including physical examination, and AEs review) will be performed. At the end of study (EOS/V4), AEs will be assessed, and patients will be asked to express their satisfaction with the BREAST-Q. All study procedures are schematized in the flowchart (section 1.2.5).

#### 1.2.1. Randomization

Considering the design of the study, a randomization procedure is not required.

#### 1.2.2. Treatment

The BCL System is a patient-matched Breast Conserving Surgery (BCS) guidance device derived from

|  |                           |                  |                |
|--|---------------------------|------------------|----------------|
|  | Form               | Form Nr.  | 1M-DMST-011-A3 |
|  | Statistical Analysis Plan | Page      | 8 of 116       |
|  |                           | Version # | 0.1            |

supine breast magnetic resonance imaging (MRI) data. The device allows the surgeon to transfer surgical cues associated with a patient's breast and breast cancer to help guide the surgeon with the tumor resection procedure. An optional web-based interactive surgical plan Visualizer will be provided, displaying a 3D model of the BCL, tumor, and chest wall with markers indicating the closest points and distances between the tumor, skin, and chest wall/muscle.

The procedure consists of three main steps as described in the BCL System IFU:

- Step 1. Pre-surgical imaging and image transfer;
- Step 2: breast tissue marking using the BCL;
- Step 3: surgery and tumor removal.

At visit 2 (V2), all the enrolled patients meeting all the inclusion and none of the exclusion criteria were treated BCS using the BCL System.

### 1.2.3. Sample Size

The positive margin rate (PMR) with the use of BCL is expected to be < 5% based on a previous study [2]. Assuming a true PMR of 3% and applying the exact or Clopper-Pearson method for a single binomial proportion then a sample size of N=35 patients who have undergone surgery with the BCL and have had a margin assessment will achieve a confidence interval with total width of 15%. The upper limit of this confidence interval (18%) is lower than the currently observed positive margin rate using the standard of care.

An exact binomial confidence interval will be calculated using the actual PMR. The withdrawal of patients before the surgery with BCL will be considered as drop-out.

Statistical power calculation was performed using SAS® software [1], version 9.4.

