## 4. Analysis Sets and Subgroups

### 4.1. Analysis sets

The data sets defined for the study in accordance with the study protocol are outlined in the following table.

|                            |   |
|----------------------------|---|
| Safety Analysis Set (SAS): | The "Safety Set" will include All patients undergoing surgery with the BCL System.  |
| Full Analysis Set (FAS):   | The "Full Analysis Set" will include All patients undergoing surgery with the BCL System.   |
| Per-Protocol Set (PPS):    | The "Per-Protocol Set (PPS)" will include all the FAS patients who (a) met all inclusion/exclusion criteria liable to affect the performance assessment, (b) did not present serious deviations of the protocol that may affect efficacy. |

Definition of major protocol deviations and selection of subjects accordingly will be performed prior to Database Lock (DBL).

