## 6. Statistical Analysis: Definitions, Derivations, Calculations and Methodology

### 6.1. Baseline Characteristics

#### 6.1.1. Disposition of Patients

##### Collected Variables:

- Was Informed Consent signed? (Yes/No) [CRF – V0]
- If Yes, Informed Consent date (dd/mmm/yyyy) [CRF – V0]
- Visit date (dd/mmm/yyyy) [CRF – V0, V1, V2, V3, V4]
- Was surgery performed? (Yes/No) [CRF – V2]
- If Yes, date of surgery (dd/mm/yyyy) [CRF – V2]
- Has the patient completed the study? (Yes/No) [CRF – EOS]
- If Yes, specify date (dd/mm/yyyy) [CRF – EOS]
- If No, specify the reason for early termination or withdrawal (Screening failure/Consent withdrawal/Adverse event/Protocol violation/Lost to follow-up/Subject non-compliance/Death/Other) [CRF – EOS]
- Date of withdrawal (dd/mmm/yyyy) [CRF – EOS]
- If Death, please specify cause of death (free text) [CRF – EOS]
- If Other, please specify (free text) [CRF – EOS]

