#### Collected Variables:

Previous radiological assessment

- Was mammogram available prior to enrollment? (Yes/No) [CRF – V0]
- If No, please specify (free text) [CRF – V0]
- If Yes, was IBC/DCIS confirmed? (Yes/No) [CRF – V0]
- Was prone MRI available prior to enrollment? (Yes/No) [CRF – V0]
- If No, please specify (free text) [CRF – V0]
- Tumor maximal diameter (mm) (number) [CRF – V0]
- Presence of satellite lesions less than or equal to 2 cm from the primary? (Yes/No) [CRF – V0]
- Was pathological analysis of diagnostic core biopsy specimens available prior to enrollment? (Yes/No) [CRF – V0]
- If No, please specify (free text) [CRF – V0]
- If Yes, IBC or DCIS? (DCIS/IBC/Both DCIS and IBC) [CRF – V0]

Supine MRI

- Was supine MRI performed? (Yes/No) [CRF – V1]
- If No, please specify (free text) [CRF – V1]
- Where images transferred to CairnSurgical? (Yes/No) [CRF – V1]
- If no, reason (free text) [CRF – V1]
- Tumor maximum diameter (cm) (number) [CRF – V1]
- Tumor volume (cm^3) (number) [CRF – V1]
- Optimal resection volume (cm^3) (number) [CRF – V1]

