#### Imputations for missing values:

|  |                           |                  |                |
|--|---------------------------|------------------|----------------|
|  | Form               | Form Nr.  | 1M-DMST-011-A3 |
|  | Statistical Analysis Plan | Page      | 28 of 116      |
|  |                           | Version # | 0.1            |

Not applicable.

|                               |          |                |
|-------------------------------|----------|----------------|
| Analysis Sets to be used for: | Tables   | SAS            |
|                               | Listings | SAS            |
|                               | Figures  | Not applicable |

Patients' data will be summarized as follows:

|   |  |
|---|--|
| Table 9. Previous radiological assessments | Frequencies table of information and results about the previous radiological assessment of the patients included in the SAS. |
|---|--|

|                             |   |
|-----------------------------|---|
| Table 10. Supine MRI | Frequencies table of information and results collected through the supine MRI for the patients included in the SAS. |
|-----------------------------|---|

Patients' data will be listed as follows:

|   |  |
|---|--|
| Listing 6. Previous radiological assessments | Listing of information and results about the previous radiological assessment of the patients. |
|---|--|

|                              |  |
|------------------------------|--|
| Listing 7. Supine MRI | Listing of information and results collected through the supine MRI. |
|------------------------------|--|

|  |                           |                  |                |
|--|---------------------------|------------------|----------------|
|  | Form               | Form Nr.  | 1M-DMST-011-A3 |
|  | Statistical Analysis Plan | Page      | 29 of 116      |
|  |                           | Version # | 0.1            |

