#### Collected Variables:

- Was surgery performed? (Yes/No) [CRF –V2]
- If No, please specify the reason (free text) [CRF –V2]  
If Yes:
- Date of surgery (dd-mmm-yyyy) [CRF –V2]
- Was Tumor specimen removed? (Yes/No) [CRF –V2]
- If No, please specify the reason (free text) [CRF –V2]  
If Yes:
- Was specimen mammogram obtained? (Yes/No) [CRF –V2]
- If No, please specify the reason (free text) [CRF –V2]
- Was tumor specimen sent to the pathologist for evaluation of the positive margins? (Yes/No) [CRF –V2]
- If No, please specify the reason (free text) [CRF –V2]
- Were positive margins detected? (Yes/No) [CRF –V2]

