#### Imputations for missing values:

|  |                           |                  |                |
|--|---------------------------|------------------|----------------|
|  | Form               | Form Nr.  | 1M-DMST-011-A3 |
|  | Statistical Analysis Plan | Page      | 32 of 116      |
|  |                           | Version # | 0.1            |

Not applicable.

|                               |          |                |
|-------------------------------|----------|----------------|
| Analysis Sets to be used for: | Tables   | FAS, PPS       |
|                               | Listings | FAS            |
|                               | Figures  | Not applicable |

Patients' data will be summarized as follows:

|   |   |
|---|---|
| Table 14. Surgery and positive margin evaluation | Frequency table of information about the surgery and the related procedures, tumor specimen handling, and evaluation of the presence of positive margins for patients in FAS and PPS. |
|---|---|

Patients' data will be listed as follows:

|  |   |
|--|---|
| Listing 8. Surgery and positive margin evaluation | Listing of all information the surgery and the related procedures, tumor specimen handling, and evaluation of the presence of positive margins for patients in FAS and PPS. |
|--|---|

Patients' data will be represented as follows:

|                                   |   |
|-----------------------------------|---|
| Figure 3. Positive margins | Bar plot displaying the proportion of patients with positive margins after surgery with BCL in FAS and PPS, respectively. |
|-----------------------------------|---|

|  |                           |                  |                |
|--|---------------------------|------------------|----------------|
|  | Form               | Form Nr.  | 1M-DMST-011-A3 |
|  | Statistical Analysis Plan | Page      | 33 of 116      |
|  |                           | Version # | 0.1            |

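### The imaging, image-transfer, surgery and device-deficiency items are tabulated only in patients undergoing BCL surgery, so these tables cannot show a BCL System failure before surgery

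*SAP*

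**What the plan says.** SAP 4.1 gives the Safety Analysis Set (SAS) and the Full Analysis Set (FAS) the same membership. Each "will include All patients undergoing surgery with the BCL System". SAP 1.2.3 adds: "The withdrawal of patients before the surgery with BCL will be considered as drop-out".

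The case report form follows the delivery of the device step by step. SAP 6.1.7 lists, at V1, whether the supine MRI was done and whether the images went to the manufacturer, each with a free-text reason if not. SAP 6.2.1 lists, at V2, whether surgery took place, again with a reason if not. SAP 6.4.5 collects device deficiencies at V1 and V2.

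The populations for reporting these items are:

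- Supine MRI and image transfer (SAP 6.1.7): "Frequencies table of information and results collected through the supine MRI for the patients included in the SAS". The listing shell is also headed SAS.
- Surgery (SAP 6.2.1): one table covering the operation, "tumor specimen handling, and evaluation of the presence of positive margins for patients in FAS and PPS". The listing shell is headed FAS.
- Device deficiencies (SAP 6.4.5): table and listing in the SAS.

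SAP 5.2 takes the whole table population as the percentage denominator unless stated otherwise. It also says that every listing covers all patients, which conflicts with the SAS and FAS headings above.

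For all patients, SAP 6.1.1 provides Tables 1 to 3, Figures 1 and 2, and Listing 1A. Its end-of-study item reads "If No, specify the reason for early termination or withdrawal". The options end with Other plus free text, and none is specific to the device.

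**The concern.** Imaging and image transfer are part of the device under study. SAP 1.2.2 makes them Step 1 of the BCL procedure, and Protocol 1.2.2 lists the MRI kits as components of the BCL System. Problems at this stage are documented: Protocol 2.11.1 traces the one inaccurate localisation among the pilot's 19 subjects to breast deformation by the MRI coil.

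A table restricted to patients who reached BCL surgery cannot show the steps that stop a patient from reaching it. Its No rows cannot fill, and a printed 100% carries no information about how reliably the system is delivered. The shells suggest that this was not intended. The supine MRI listing is headed SAS, yet it contains a mock row with MRI not done and images not sent, each with a reason. Such a patient could have no BCL and could not be in the SAS.

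The restriction also affects safety reporting. A deficiency recorded at V1 in a patient who is never operated on with a BCL appears in no device-deficiency table.

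**Working it through.** **The plan's own figure.** SAP 1.2.3 and Protocol 2.5.1 state a total width of 15% for the exact 95% interval at N = 35 and a true rate of 3%. The Clopper-Pearson limits are the 2.5% quantile of Beta(x, n−x+1) and the 97.5% quantile of Beta(x+1, n−x).

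- x = 0.03 × 35 = 1.05: 0.09% to 15.14%, width 15.05 points.
- x = 1: 0.07% to 14.92%, width 14.84 points (from unrounded limits).

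The stated width reproduces. The stated upper limit of 18% does not; it equals 3% + 15%. That is a separate matter and does not affect this point.

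**What the tables can print.**

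1. A patient is in the SAS or FAS only if she undergoes surgery with the BCL (SAP 4.1).
2. Surgery performed, tabulated in the FAS and its per-protocol subset, is therefore 100% by definition, apart from missing entries.
3. The BCL is made from the supine MRI (SAP 1.2), so no patient can have BCL surgery without the scan and its transfer. Both items are about 100% in the SAS in practice.
4. A failure at any of these steps removes the patient from numerator and denominator together.

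**Size.** Neither document gives a pre-surgery failure rate. Assume k enrolled eligible patients are lost through BCL System failure, with no other losses. Two readings of 35 are possible. SAP 1.2.3 means 35 operated on with margins assessed, so delivery = 35/(35 + k). The protocol supplied means 35 enrolled (synopsis), with no replacement (2.5.5), so delivery = (35 − k)/35.

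| k (assumed) | 35 operated: delivery (exact 95% CI) | 35 enrolled: delivery (exact 95% CI) | Current tables |
|---|---|---|---|
| 1 | 35/36 = 97.2% (85.5–99.9) | 34/35 = 97.1% (85.1–99.9) | 100% |
| 3 | 35/38 = 92.1% (78.6–98.3) | 32/35 = 91.4% (76.9–98.2) | 100% |
| 5 | 35/40 = 87.5% (73.2–95.8) | 30/35 = 85.7% (69.7–95.2) | 100% |
| 7 | 35/42 = 83.3% (68.6–93.0) | 28/35 = 80.0% (63.1–91.6) | 100% |

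The last column does not depend on k.

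**What the all-patients outputs add.** Table 1 gives reasons for exclusion from each set, Table 2 withdrawal reasons, and Table 3 attendance by visit including surgery. Listing 1A has columns for surgery performed, the reason for non-completion and the free text under Other. The number lost before surgery can therefore be recovered, and a device reason can be printed if a site writes one. No output groups these reasons as system-related, and none gives a delivery proportion.

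**The case against.** The strongest reply is that conditioning on BCL use is what the study set out to do. The primary objective concerns margins when the system guides the surgeon, and the endpoint is positive margins after partial mastectomy with the BCL (Protocol 2.2 and 2.3.1). A patient without that operation has no such margin, and feasibility of imaging or manufacture is not a named endpoint. This stands. It rules out treating the FAS positive margin rate as wrong, or requiring a composite of technical failure and positive margin. A composite would also score as a failure a patient whose margins were clear by another method.

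A reader might infer that the SAP formally counts a BCL that could not be made or used as a drop-out. It does not say so. SAP 1.2.3 speaks of withdrawal; that a failed BCL would fall among these losses is an inference from the set definitions. SAP 4.1 also says undergoing, not completing, so a BCL abandoned in theatre or found not to fit may leave the patient in the FAS. The documents do not settle this.

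A reader might also infer that failures are hidden. They are not, given Tables 1 to 3, Figures 1 and 2, Listing 1A and the free text under Other. If SAP 5.2 prevails over the listing headings, the reason fields would be listed for everyone. Even so, SAP 5.2 covers no table, and the losses remain unlabelled and unquantified.

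**Conclusion.** The point holds as one of reporting. The tables of supine MRI, image transfer, surgery performed and device deficiencies use populations that exclude any patient in whom the system failed before surgery. The first three therefore print about 100% whatever happened. With 1 to 7 failures the delivery rate would be 97.2% to 83.3% (35 operated) or 97.1% to 80.0% (35 enrolled). The counts are assumptions, and the actual number may be zero.

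The fixed 100% belongs to process items; the SAP does not present it as success on the primary endpoint. One limit applies: the SAP is written from protocol version 2.0 of November 2023 (SAP 1.1), which is not among the documents supplied, so its withdrawal rules and its meaning of 35 could not be checked. The set definitions and table populations are in the SAP itself, so the core does not depend on that version. This is a cheap improvement.

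**What to change.** 1. In SAP 6.1.7, 6.2.1 and 6.4.5, tabulate and list the supine MRI, image-transfer, surgery-performed and device-deficiency items on all enrolled eligible patients, and reconcile the listing headings with SAP 5.2. Protocol 2.6 defines enrolment as meeting all the criteria, so screening failures stay out. A denominator of patients who reached V1 or had the scan would not do, because V1 is the MRI visit and would again condition on that step.
2. Before database lock, use the existing reason and Other free-text fields to classify each pre-surgery loss as BCL System-related (imaging, transfer, manufacture or delivery) or not.
3. Beside the positive margin rate, report patients undergoing BCL-guided surgery over all enrolled eligible patients, with an exact 95% interval, and give the split from step 2.

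The FAS positive margin rate stays primary. No composite and no new case report form code is needed. The SAP is at version 0.1, and Protocol 2.5.2 calls for version 1.0 before database lock, so the change is one of wording and table populations. The cost is a little extra tabulation and a possibly less favourable figure beside the margin rate.

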### 1.2.4. Blinding

Considering the design of the study a blinding/unblinding procedure is not required.

|  | Form                      | Form Nr.  | 1M-DMST-011-A3 |
|--|---------------------------|-----------|----------------|
|  | Statistical Analysis Plan | Page      | 9 of 116       |
|  |                           | Version # | 0.1            |

### 1.2.5. Flow Chart of the Study

The study visits and related procedures are summarized in the flowchart below.

| Determinations   | Screening & Enrollment (V0) A | Visit 1 (V1)
Supine MRI A | Visit 2 (V2)
Surgery           |                    | Visit 3 (V3)
Follow-Up     | Visit 4 (V4)
End Of Study (EOS) |
|--|--|---|-----------------------------------|--------------------|-------------------------------|------------------------------------|
|  | Within 15-30 days before V1              | Day 0 A                      | Within 10-40 days from supine MRI | Prior to discharge | 2 weeks ± 7 days post surgery | 6 weeks ± 7 days post surgery      |
| ICF A   | X  |   |                                   |                    |                               |                                    |
| Inclusion/Exclusion criteria   | X  |   |                                   |                    |                               |                                    |
| Medical history B   | X  |   |                                   |                    |                               |                                    |
| Demographic data (including age, smoking habits and alcohol use)         | X  |   |                                   |                    |                               |                                    |
| Vital signs (BP, HR, O 2 saturation)                          | X  | X                                       | X                                 | X                  | X                             |                                    |
| Physical examination C  | X  |   |                                   | X                  | X                             |                                    |
| Blood samples (laboratory parameters) D                       | X  |   |                                   |                    |                               |                                    |
| Urine pregnancy test to all women of childbearing potential E | X  |   |                                   |                    |                               |                                    |
| Radiological assessment F                                     | X  |   |                                   |                    |                               |                                    |
| Supine MRI   |  | X A                          |                                   |                    |                               |                                    |
| Prone MRI  | X A                           |   |                                   |                    |                               |                                    |
| Provide tumor specimen to pathological lab G                  |  |   | X                                 |                    |                               |                                    |
| BCS with BCL H  |  |   | X                                 |                    |                               |                                    |
| 5 Likert Scale (completed by PI) I                            |  |   | X                                 |                    |                               |                                    |
| BREAST-Q   |  |   |                                   |                    |                               | X                                  |
| Adverse events (AEs)   | X  | X                                       | X                                 | X                  | X                             | X                                  |
| Concomitant medications  | X  | X                                       | X                                 | X                  | X                             | X                                  |
| Device deficiencies/incidents monitoring                                 |  | X                                       | X                                 |                    |                               |                                    |

